## 10.0 Subject Selection and Enrollment

After being informed of the nature of the study, the subject will sign a written informed consent form (ICF) that has been approved by the appropriate IRB of the respective clinical site. Enrollment of up to 100 subjects is planned.

Subjects' participation in the study will last approximately 8 days, including the procedure day, five days prior for bowel preparation, and the follow up period.

Subjects will be considered for the study if they meet the specific inclusion/exclusion criteria. The criteria for enrollment must be followed explicitly.

Enrollment completion is expected to take place up to 12 months following IRB approval of the study.

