## 11.0 Study Procedures

### 11.1.1 Screening and Informed Consent (Visit 1)

Subjects participating in the study may be recruited from investigator's patients' pool.

A screening/baseline visit will be performed within 30 days prior to the scheduled Pure-Vu procedure to assess preoperative eligibility. In the event that the screening and eligibility assessment takes place more than 30 days prior to the planned procedure date, the investigator should contact the subject prior to the procedure date to assure there is no change in the subject's medical condition.

At the screening visit, subjects will be approached to obtain written informed consent prior to any study specific procedures being performed. The purpose of the study and the benefits and risks of the procedures will be explained to the subject and the consent process must be documented accordingly in the medical record. Subjects who agree to study participation must sign an IRB-approved ICF. Subjects will be informed that their participation in this study is voluntary and they may refuse to participate or discontinue from the study at any time. Subjects will be given the opportunity to ask the investigator questions so that they are adequately informed about the research. A copy of the signed informed consent must be provided to the subject and the informed consent process will be documented in source documents.

If new information becomes available that may affect a subject's decision to continue to take part in the study, this information will be discussed with the subject by the investigator.

Document title:	Document No.	Version	Page 26 of 61
Optimizing the Preparation Regime Prior to Colonoscopy Procedure with Pure-Vu System	CL00042	1.0	

The following assessments will be performed within 30 days prior to the scheduled procedure and the results recorded on the appropriate subject CRFs:

- Verification of eligibility criteria and subject risk per guidelines
- Demographics (age, gender, height, weight)
- Surgical and medical history (prior abdominal surgery, GI symptoms)
- General medical history will be assessed based on the subject's clinical condition

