#### **11.1.3 Screen Failures**

A subject is considered enrolled in the study when the ICF is signed. Only subjects who receive study-assigned procedures will be followed. Subjects who provide study consent, but then are determined to be ineligible prior to randomization will be considered screening failures and will

Document title:	Document No.	Version	Page 27 of 61
Optimizing the Preparation Regime Prior to Colonoscopy Procedure with Pure-Vu System	CL00042	1.0	

not require additional study follow-up. The reason for the screening failure will be clearly documented, the Subject "Enrollment and Visit Log" will be completed and the subject eligibility section in visit 1 as well as a "Study Completion" form will be completed in the CRF.

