#### **11.1.5 Colonoscopy procedure (Visit 2)**

##### Pre-Examination Procedures

- Verify eligibility checked and informed consent was obtained after explaining all risks, benefits, and alternatives to the candidate.
- Verify that the research assistant has collected completed diaries from the subject.
- Verify all background/clinical information, demographic and medical history was documented

Note: Subjects that did not take the bowel preparation or failed to complete the bowel preparation will not undergo the procedure and will be excluded from the study.

- Verify all connections and assembles are properly attached (see Instructions for Use)
- Verify device works properly (see Instructions for Use)
- Place and prepare the subject for the procedure as per standard colonoscopy.
- Perform a digital rectal exam as per standard colonoscopy, evaluate the adequate level of the preparation and start the colonoscopy procedure with the Pure-Vu System as per standard of care.

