## 12.4 Effectiveness Analyses

### Safety Analysis

The secondary endpoint is to evaluate the Device related adverse event and the overall adverse events rate. The safety analysis set will consist of all patients who were enrolled into the study.

Individual listings of adverse events including type of device, adverse events (reported term), seriousness, duration, relationship to the study device, severity and the adverse events outcome will be provided for the total population and per study arm. AEs will be summarized using frequency counts and percentages per study arm.

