## **12.5 Analysis Populations**

Cases withdrawn prior to the Pure-Vu procedure and those with technical failure will be excluded from the efficacy analysis. All patients who undergo bowel preparation will be included in the safety analysis.

Individual listings of withdrawal / failure including descriptive information will be provided.

In addition, in cases of incomplete procedure (i.e., the entire colon is not visualized); the overall BBPS per patient will be evaluated based on the colon segments that were visualized.

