### 13.1 Adverse Event (AE)

An AE is any untoward medical occurrence, unintended disease or injury, or untoward clinical signs (including abnormal laboratory findings) in subjects, whether or not related to the investigational medical device.

This definition includes events related to the investigational medical device or the comparator and the procedures involved.

AEs will be collected starting from the time subject is enrolled until the follow-up period is completed.

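### The device-related adverse event rate has no denominator restricted to patients in whom Pure-Vu was used, and the passages defining the safety set conflict

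*Protocol*

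**What the plan says.** The safety part of section 12.4 names two rates: "The secondary endpoint is to evaluate the Device related adverse event and the overall adverse events rate". The denominator follows directly: "The safety analysis set will consist of all patients who were enrolled into the study". Section 11.1.3 defines the term: "A subject is considered enrolled in the study when the ICF is signed". Section 12.4 also calls for counts and percentages by arm, and gives no separate denominator for device-related events.

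Section 12.5 defines the set differently: "All patients who undergo bowel preparation will be included in the safety analysis".

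Section 11.1.5 says that subjects who did not take the preparation or "failed to complete the bowel preparation will not undergo the procedure"; the same sentence goes on to exclude them from the study. Section 11.1.3 limits follow-up to subjects who receive study-assigned procedures.

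On timing, section 13.1 states: "AEs will be collected starting from the time subject is enrolled until the follow-up period is completed". Section 11.1.1 places the consent visit: "A screening/baseline visit will be performed within 30 days prior to the scheduled Pure-Vu procedure", and allows a longer interval if the subject is contacted before the procedure. Sections 9.0 and 11.1.1 start the preparation five days before the colonoscopy. Section 10.0 says that "participation in the study will last approximately 8 days". As extracted, the adverse event row of the Appendix A schedule is marked only under Visit 2.

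**The concern.** A patient in whom the Oversleeve was never inserted cannot have a device-related event. Counting such patients in the denominator lowers the device-related rate, always in the device's favour. Choosing between the sets in 12.4 and 12.5 does not cure this, because neither is limited to exposed patients. Safety is the first secondary objective in section 8.2.

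The onset window affects a different quantity. The end of section 5.1 lists adverse event rates among the outcomes to be compared between the two preparations. Events before day −5 arise before either regimen has begun, yet the tables as described would place them under Prep A or Prep B.

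**Working it through.** The protocol states no adverse event rate, so there is no planned figure to reproduce.

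**Who can be unexposed under each passage**

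- Section 12.4 (consent signed): screen failures, withdrawals before the procedure, and patients who did not take or complete the preparation. Screen failures have no arm, so they can enter only a total-population rate; the per-arm effect comes from randomised patients who never had the procedure.
- Section 12.5 (underwent preparation): patients who began the preparation but did not complete it, or who withdrew before the procedure.
- Section 11.1.5 (excluded from the study): if this governs, preparation non-completers leave the safety set. That contradicts 12.4, and it contradicts 12.5 for those who began the preparation. It would also drop anyone who stopped because of the nausea or vomiting that section 7.2 anticipates.

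**Effect on the device-related rate**

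Let x be the number of patients with a device-related event, N the number in the set and f the unexposed share.

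- Reported rate: x / N
- Rate among exposed: x / [N(1 − f)]
- Ratio of reported to exposed rate: 1 − f

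With zero events among n patients, the one-sided 95% upper bound is 1 − 0.05^(1/n). N = 100 is the planned maximum. The two events and all values of f are assumptions. The 38% is the section 5.1 figure for non-completion of bowel preparation generally.

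| f | Exposed | 2 events, reported | 2 events, exposed | Zero-event bound on exposed |
|---|---|---|---|---|
| 0 | 100 | 2.0% | 2.0% | 2.95% |
| 10% | 90 | 2.0% | 2/90 = 2.2% | 3.27% |
| 20% | 80 | 2.0% | 2/80 = 2.5% | 3.68% |
| 38% | 62 | 2.0% | 2/62 = 3.2% | 4.72% |

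On 100 patients the zero-event bound would be reported as 2.95% whatever the value of f.

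**Effect of the onset window**

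The 30 days in 11.1.1 run to the procedure. The interval before the day −5 diet is therefore 30 − 5 = 25 days, and longer only where the allowance for later procedures is used.

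Let p be an arm's true risk from the start of preparation, and b an independent background risk between consent and preparation, equal in both arms.

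- Observed risk: 1 − (1 − p)(1 − b)
- Observed difference: (1 − b) × true difference

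Assume, for illustration, true risks of 30% and 15%.

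| b | Arm rates | Difference (points) | Ratio |
|---|---|---|---|
| 0 | 30.0% / 15.0% | 15.0 | 2.00 |
| 5% | 33.5% / 19.3% | 14.3 | 1.74 |
| 10% | 37.0% / 23.5% | 13.5 | 1.57 |
| 20% | 44.0% / 32.0% | 12.0 | 1.38 |

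Each arm's rate rises, while the contrast shrinks.

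**Participation length**

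Section 10.0 counts five preparation days, the procedure day and follow-up. With the 48-hour contact this is 5 + 1 + 2 = 8 days. It leaves out the interval from consent over which 13.1 collects events.

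**The case against.** The exclusion sentence in 11.1.5 could be read as removing non-completers from every analysis. The dilution would then be smaller, and the defect mainly a contradiction. This stands in part: the text does not settle who is counted. But both passages that define the safety set retain such patients, at least once they have begun the preparation, and neither carries that exclusion.

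At 10% unexposed the change is 2.0% against 2.2%, small in an unpowered pilot that also reports counts. This stands, and it limits the weight of the point. The 38% is no forecast: section 5.1 ties it to palatability and large volumes, and this trial uses reduced regimens.

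Denominators and onset windows are often left to the statistical analysis plan, which is not among the documents reviewed. Here, however, the protocol itself fixes the safety set, twice and differently.

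On the window, collecting events from consent is sound practice. The planned summary is descriptive, with no test of adverse events between arms. No contact is scheduled between Visit 1 and the preparation except where screening was more than 30 days earlier, and the diary logs cover only day −1 and the procedure day. Section 13.10 also discounts pre-existing conditions that have not worsened. All this suggests that few early events would be recorded.

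Three stronger readings are tempting but unsupported:

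- A reader might infer that both safety rates are diluted. Early events raise each arm's rate; only the contrast is diluted.
- A reader might infer that background events swamp the comparison, because with consent at day −30 some 25 of 33 days (25 + 8), or 76%, precede the preparation. That is a share of days, and the protocol gives no background event rate.
- A reader might infer that many counted events precede randomisation. Appendix A puts consent and randomisation at the same visit.

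**Conclusion.** The point holds for the device-related rate. Sections 11.1.5, 12.4 and 12.5 conflict, and under either stated safety set unexposed patients can enter the denominator, so the rate is understated by the factor (1 − f). The likely size is modest: 2.0% in place of 2.2% at an assumed f of 10%. At 38% it would be 2.0% in place of 3.2%, which should be read as an upper illustration. If no events occur, the effect lies in the upper bound: 2.95% on 100, against 3.27% on 90 or 4.72% on 62. All of this rests on assumed event counts and an f that the protocol does not give.

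The onset window is a secondary matter. It inflates both arms' rates and can reduce the contrast, by an amount that depends on an unknown background risk. The 8-day statement and the Appendix A row are inconsistencies to reconcile and do not by themselves bias a result.

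**What to change.** 1. Reconcile 11.1.5, 12.4 and 12.5, so that one passage says who is in the safety set and whether preparation non-completers are in it.
2. In 12.4, compute device- and procedure-related adverse event rates over patients in whom the Oversleeve was inserted.
3. For overall adverse events, use all randomised patients who started the preparation, by arm, whether or not they completed it.
4. Keep collection from consent. In the per-arm tables, count events with onset or worsening from the start of preparation, and list earlier events separately. The day −5 diet restriction is common to both arms, so this limit still includes some days on which the regimens do not differ.
5. Reconcile the window in 13.1 with Appendix A (as extracted) and with the 8-day statement in 10.0.

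The cost is a few lines of text and one form change. The adverse event form in Appendix F already has a start date, but its relationship item refers to the study. It must record relation to the device, which the listings in 12.4 already require, and relation to the procedure for item 2. The forms shown have no field for the start of preparation, so day −5 would be derived from the scheduled procedure date, which must then be held for patients who never reach the procedure. The device-related rate will look slightly less favourable.

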### Cecum intubation rate

Completion of colonoscopy with the Pure-Vu System is defined from insertion of colonoscope to visualization of the cecum. Cecal intubation will be evaluated by the percent of colonoscopy procedures that reached the cecum.

Proportion (Chi-square or Fisher's exact) tests will be performed in order to compare between the two preparation procedures for the following endpoint based on binary measure.

In addition, frequency counts, percentages, and 95% confidence intervals will be provided.

### Time analysis

T-tests for continuous variables will be performed in order to evaluate the difference between the two preparation procedures for the following endpoints:

- Time to Cecum- defined as the duration from colonoscope insertion to visualization of the cecum.

Document title:	Document No.	Version	Page 31 of 61
Optimizing the Preparation Regime Prior to Colonoscopy Procedure with Pure-Vu System	CL00042	1.0	

- Total Procedure time- defined as the time from colonoscope insertion to removal. (guide: >6 minutes withdrawal time)

These endpoints will be summarized using descriptive statistics, including number of subjects, mean, median, standard deviation, minimum, and maximum.

### **Patient Satisfaction**

Patient satisfaction will be evaluated by a questionnaire (Appendix E). The patient will be asked to fill-in a questionnaire and include their feedback on the procedure including specific aspects related to the preparation regime.

Patient satisfaction will be summarized in a table via descriptive statistics by data type. Chi-square or Fisher's exact test, as appropriate, will be performed in order to compare the patient satisfaction between the two study arms.

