## 5.1 Background

Colorectal cancer is the third most common cancer in men and the second most common cancer in women worldwide (2). In the United States, approximately 134,490 new cases are estimated for 2016 with approximately 49,190 deaths (8.0% of all cancer deaths) (3). Because colorectal cancer tends to develop slowly, screening and early detection can significantly reduce both the incidence and associated mortality of the disease (4).

Methods for the evaluation of subjects with suspected colonic disease include optical colonoscopy (OC) and radiologic imaging such as double contrast barium enema (DCBE) or computed tomography (CT) colonoscopy (5). While OC is considered the gold standard, patient acceptance rates are low due to perceived discomfort.

A key factor for ensuring high quality colonoscopy and successful screening is good colon preparation. Bowel preparation prior to colonoscopy is one of the major barriers to patient compliance in screening colonoscopy estimated as many as 38% of patients do not complete the bowel preparation due to palatability and/or intolerance to the large volume. Inadequate preparation is a major obstacle for achieving a high-quality colonoscopy (6). Poor bowel preparation prolongs overall screening and procedure time, decreases cecal intubation rates,

Document title:	Document No.	Version	Page 13 of 61
Optimizing the Preparation Regime Prior to Colonoscopy Procedure with Pure-Vu System	CL00042	1.0	

reduces the detection of colorectal neoplasms, increases complication rates and leads to return visits for screening which in turn leads to increased costs (7-12)

Despite the importance of good preparation, up to 25% of patients arrive for colonoscopy with inadequate bowel preparation (13) .

Pure-Vu System enables colon cleansing during standard colonoscopy using a standard colonoscope with a length of 1630mm – 1710mm and a diameter between 12.8mm – 13.7mm. The Oversleeve device, which fits over the colonoscope and is connected to an external workstation, generates fluid jets to break up the feces. The fecal matter & fluids are removed through the evacuation channels of the Oversleeve device into an external waste receptacle.

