### 8.2 Secondary objectives:

- To evaluate the safety related to the Pure-Vu System in both study arms.
- To evaluate the time to reach the Cecum in Pure-Vu procedures in both study arms.
- To evaluate the total procedure time with Pure-Vu in both study arms.
- To evaluate the cecal intubation rate with Pure-Vu in both study arms.
- To evaluate patients' satisfaction with Pure-Vu procedure in both study arms.
- To evaluate Pure-Vu user satisfaction with Pure-Vu procedure in both study arms.

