#### 9.2 Secondary Endpoints

The following secondary outcomes will be determined:

- AEs

Document title:	Document No.	Version	Page 23 of 61
Optimizing the Preparation Regime Prior to Colonoscopy Procedure with Pure-Vu System	CL00042	1.0	

- Rate of procedures where the cecum was visualized.
- Time to reach the cecum.
- Total procedure time.
- User satisfaction will be evaluated by a questionnaire filled-in by the physicians and nurses who conduct the procedures and assemble the Pure-Vu System.

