### 23.0 Appendix E – Case Report Form (filled-in by the patient)

**Pure-Vu™**  
**Patient Satisfaction Questionnaire**

**Procedure Date / Patient ID Number:** \_\_\_\_\_ / \_\_\_\_\_

**Physician Name:** \_\_\_\_\_

*The patient will answer the following questions prior the colonoscopy procedure*

Question #1	Yes	No
Was this your first colonoscopy?		

Question #2	Very Easy	Easy	Tolerable	Difficult	Very Difficult
How tolerable did you find the low fiber diet in this bowel preparation process?					
How tolerable did you find the bowel cleansing purgative in this bowel preparation process?					
How disruptive was the bowel preparation process to your normal activities?					

Question #3
If you could change two things in the bowel preparation process, what would they be?
1
2

CONFIDENTIAL

Document title:  Optimizing the Preparation Regime Prior to Colonoscopy Procedure with Pure-Vu System	Document No.  CL00042	Version  1.0	Page 53 of 61
---	------------------------------------	---------------------------	------------------

***The patient will answer the following questions after the colonoscopy procedure during the follow up phone call (will be filled by the site study coordinator)***

Question #4	Yes	No
Based upon your experience with Pure-Vu, would you recommend Pure-Vu to your friends and family members who need a colonoscopy?		

Please explain why:

---

---

Question #5	Yes	No
Would you request Pure-Vu for your next colonoscopy?		

Question #6	Yes	No
Would you request Pure Vu again for your next colonoscopy if it cost \$300?		

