## 24.0 Appendix F – Case Report Form (filled-in by the physician)

**Site No.      Subject No.      Subject Initials**

Study arm:  Magnesium Citrate 10 oz  Magnesium Citrate 15 oz

**Physician Name:** \_\_\_\_\_

Date subject signed the informed consent form: \_\_\_\_ / \_\_\_\_ / \_\_\_\_  
DD MM YY

Date investigator/designee signed the informed consent form: \_\_\_\_ / \_\_\_\_ / \_\_\_\_  
DD MM YY

Did the subject satisfy all enrollment criteria?  Yes  No (if No, please specify which criterion was not met)

**Patient Gender / Age:** \_\_\_\_\_ / \_\_\_\_\_

**Patient Height (cm) / Weight (kg):** \_\_\_\_\_ / \_\_\_\_\_

Please check all indications that apply for the patients' colonoscopy	Please Check
Screening	
Bleeding	
Polyp surveillance	

CONFIDENTIAL

Document title:  Optimizing the Preparation Regime Prior to Colonoscopy Procedure with Pure-Vu System	Document No.  CL00042	Version  1.0	Page 57 of 61
---	------------------------------------	---------------------------	---------------

IBD surveillance	
Family history (1st degree relative)	
Anemia	
Other: Please specify	

Prescribed Prep	Completed Yes / No
Magnesium Citrate 10oz:	
Magnesium Citrate 15oz:	

	HH : MM
Colonoscopy start time	
Time cecum reached	
Time colonoscopy ended	

Please rate the bowel prep	BBPS Rating Prior to Use of Pure-Vu (0 - 3)	BBPS Rating After Use of Pure-Vu (0 - 3)
Descending colon		
Transverse colon		
Ascending colon		

Comments: \_\_\_\_\_

Document title:  Optimizing the Preparation Regime Prior to Colonoscopy Procedure with Pure-Vu System	Document No.  CL00042	Version  1.0	Page 58 of 61
---	------------------------------------	---------------------------	------------------

	Sigmoid / Descending	Transverse	Ascending
If the cecum was not reached during the colonoscopy procedure, please indicate the furthest anatomical landmark reached			

If cecum not reached, please indicate the reason	Please Check
Poor bowel cleanliness	
Patient intolerance / discomfort	
Clinical and anatomical (such as stricture, redundant colon, etc.)	
Other: Please specify	
_____	
_____	
_____	

Usability	Excellent	Good	Acceptable	Difficult	Unacceptable
Ease of colonoscope advancement with Pure-Vu					
Ease of navigating colonoscope with Pure-Vu					
Torque ability of colonoscope with Pure-Vu					
Ease of sigmoid passing					
Ease of retroflex					

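### The between-arm comparison of prep tolerability will in effect rest on patients who finished the prep, and prep completion, already on the CRF, is not summarised by arm

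*Protocol*

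**What the plan says.** - **Who leaves.** Protocol 11.1.5 states that subjects who did not take the prep, or who "failed to complete the bowel preparation will not undergo the procedure and will be excluded from the study".
- **What is compared.** Section 12.4 (Patient Satisfaction) plans a chi-square or Fisher's exact test that "will be performed in order to compare the patient satisfaction between the two study arms". It says the questionnaire covers aspects of the preparation. It names no population and gives no rule for patients removed under 11.1.5.
- **The tolerability item.** Appendix E, Question 2, asks "How tolerable did you find the bowel cleansing purgative in this bowel preparation process", on five levels from Very Easy to Very Difficult. Its timing instruction is "The patient will answer the following questions prior the colonoscopy procedure". The questionnaire is handed out at Visit 1 (11.1.1 and Appendix A).
- **Completion.** Appendix F has a field "Completed Yes / No" for each of the two regimens. Completion appears in none of the objectives (8.2), the endpoints (9.2) or the planned analyses (12.3, 12.4). The nearest item in 9.2, "Rate of procedures where the cecum was visualized", concerns the colonoscopy and not the prep.
- **Related objective.** Section 8.2 includes "To evaluate patients' satisfaction with Pure-Vu procedure in both study arms".
- **Background.** Section 5.1 says of bowel preparation in general that "as many as 38% of patients do not complete the bowel preparation due to palatability and/or intolerance to the large volume".

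**The concern.** Finishing the prep happens after randomisation and can depend on the regimen assigned. A patient who stops because the purgative is intolerable is the one whose answer to Question 2 would be worst, and that patient leaves the study. If one arm loses more such patients, its remaining answers look better than the regimen deserves, and the two arms move closer together.

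The study's purpose is to find the optimal regimen, and the arms differ in the volume of purgative and clear liquid. Non-completion is the most direct sign that a regimen is hard to take, and section 5.1 itself links it to palatability and volume. Yet the protocol plans no comparison of it. A reader of the results could see similar tolerability scores without being shown how many patients in each arm never reached the comparison.

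**Working it through.** The protocol has no figure to reproduce: 12.1 disclaims any sample size calculation, and no completion rate by arm is given. The check has two parts.

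**1. Does any planned analysis cover the gap?**
- 12.5 lists withdrawals and failures individually, and 10.3 requires the reason to be recorded. A reader could count them, but no comparison by arm is planned.
- 12.5 puts everyone who undergoes prep in the safety analysis, and 12.4 counts adverse events by arm. Stopping because of taste or volume need not be recorded as an adverse event.
- 12.2 allows an intention-to-treat analysis only where judged necessary and on data already gathered. It cannot use answers that were never collected.

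None of these compares completion by arm.

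**2. How large could the effect be?**

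Assumed inputs: 50 patients per arm (half of the maximum of 100); non-completion a and b in the two arms, from 5% to 38%; the same share q = 15% of completers in each arm rating the prep Difficult or Very Difficult.

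Intolerance over all randomised patients = a + (1 − a) × q, and likewise for b. With q equal in both arms, the completers-only difference is 0 by construction, and the all-randomised difference is (a − b) × (1 − q).

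Example, 38% v 20%: 0.38 + 0.62 × 0.15 = 0.473 and 0.20 + 0.80 × 0.15 = 0.320, a difference of 0.153. Completers number 50 × 0.62 = 31 and 50 × 0.80 = 40.

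| Non-completion | All randomised | Difference (points) | Completers only | Power to detect the completion difference |
|---|---|---|---|---|
| 38% v 30% | 40.5% to 47.3% | 6.8 | 0 | 0.13 |
| 38% v 20% | 32.0% to 47.3% | 15.3 | 0 | 0.51 |
| 38% v 10% | 23.5% to 47.3% | 23.8 | 0 | 0.92 |
| 20% v 10% | 23.5% to 32.0% | 8.5 | 0 | 0.29 |
| 10% v 5% | 19.3% to 23.5% | 4.3 | 0 | 0.16 |

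Power is for a two-sided 0.05 test. With q = 20%, the 20% v 10% row becomes 0.36 v 0.28, or 8 points.

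**Less extreme model.** Equal q is a strong assumption, because the worse regimen should also be rated worse by those who finish it. Suppose burden is normally distributed and shifted between arms, patients above a high threshold stop, and those above a lower threshold rate the prep difficult. Set the lower threshold so that 45% of the better arm either stop or find it difficult. Then:

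| Non-completion | All randomised (points) | Completers only (points) |
|---|---|---|
| 38% v 30% | 8.7 | 3.9 |
| 38% v 20% | 20.9 | 13.8 |
| 38% v 10% | 35.2 | 29.2 |

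The gap is reduced in every case and erased in none.

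**Precision of a completion comparison.** At 20% v 10% with 50 per arm, SE = √(0.20 × 0.80/50 + 0.10 × 0.90/50) = √0.0050 = 0.071. The 95% CI is 10 ± 1.96 × 7.1, about 10 ± 14 points. That supports a descriptive estimate and not a test.

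**The case against.** The strongest reply is that no section restricts the tolerability comparison to completers. Section 12.4 names no population, and the exclusion of early withdrawals in 12.5 applies only to efficacy. The questionnaire is in the patient's hands from Visit 1, Appendix A marks it during colon preparation as well as at Visit 2, and Question 2 is answered before the procedure. A non-completer may already have filled it in. All of that is correct. The restriction is the practical consequence of excluding these patients under 11.1.5, and a reader who infers a stated completers-only rule goes further than the text. What remains is that nothing says their answers are collected or kept.

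Second, an analysis set for a supporting questionnaire can be left to an SAP. That holds for the wording of the set. It does not hold for data collection, since an SAP cannot recover answers from patients already excluded.

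Third, a reader might infer that the worse regimen will look as good as the other. The documents do not support this. The distortion needs non-completion to differ by arm, and the zero in the first table comes from assuming equal ratings among completers. The 38% is a general upper figure for bowel preparation, linked partly to large volumes. Both regimens here are reduced, so it may overstate non-completion.

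Fourth, sections 7.2 and 7.4 argue lower burden against standard preparation, not between these two arms, and patient satisfaction is not in the 9.2 list. That stands, and it limits the weight of the point. The comparison is nevertheless planned in 12.4, so it should be done on a sound basis.

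**Conclusion.** The point holds as a conditional one. Followed as written, 11.1.5 and 12.4 together make the tolerability comparison depend on finishing the prep, and completion by arm is reported nowhere. If non-completion differs between arms and is mainly due to intolerance, the difference in tolerability is understated.

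Under equal ratings among completers, the hidden difference runs from 4.3 points (10% v 5% non-completion) to 23.8 points (38% v 10%). Under the continuum model, 20.9 points shrink to 13.8 at 38% v 20%. Every rate by arm is an assumption. If non-completion is the same in both arms, there is no reason to expect this distortion.

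The matter concerns a secondary comparison in an openly unpowered pilot. It is still worth correcting, because the regimen comparison is meant to inform later studies and the main item needed is already on the CRF.

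**What to change.** In 12.4, with a cross-reference in 11.1.5:

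1. Report prep completion by arm over all randomised patients, with a 95% CI for the difference. Label it descriptive. Say how patients who withdrew before starting the prep are counted.
2. State that Appendix E Questions 1–3 are collected and kept from everyone who took any prep, including those who then do not undergo the procedure. Have the CRF completion field filled in for them too.
3. Compare Question 2 in that set. As sensitivity analyses, repeat it in completers only, and with all non-completion counted as the worst grade. Counting all non-completion avoids needing a reason that the yes/no field does not hold.

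The cost is a few extra questionnaires, on arrival or by telephone, and one table. The clinical rule on who undergoes the procedure does not need to change.
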